## **12.9 Adverse Events**

### ***12.9.1 Definitions***

#### Adverse Events:

An AE is “any untoward medical occurrence in a subject or clinical investigation subject administered a pharmaceutical product and which does not necessarily have a causal relationship with this treatment (International Conference on Harmonisation [ICH] E2A).” Study drug includes both the investigational drug under evaluation and the comparator drug or placebo. Medical conditions that were present before starting study drug are only considered AEs if they worsen after the subject has started the study drug. Abnormal laboratory values or test results constitute AEs only if they induce clinical signs or symptoms, are considered clinically significant, or require treatment. All medical and psychiatric conditions (except those related to the indication under study) present at screening will be documented in the medical history CRF. Changes in these conditions and new symptoms, physical signs, syndromes, or diseases should be noted on the AE CRF page during the rest of the study. Clinically significant laboratory abnormalities should also be recorded as AEs. Surgical procedures that were planned before the subject enrolled in the study are not considered AEs if the conditions were known before study inclusion; the medical condition should be reported in the subject’s medical history.

#### Adverse Drug Reaction:

In the pre-approval clinical experience with a new medicinal product: “all noxious and unintended responses to a medicinal product related to any dose should be considered an Adverse Drug Reaction (ADR).” The phrase “responses to a medical product” means that a causal relationship between a medical product and an AE is at least a reasonable possibility, i.e., the relations cannot be ruled out.

Regarding marketed medicinal products, a well-accepted definition of an adverse drug reaction in the post-marketing setting is found in WHO Technical Report 498 [1972] and reads as follows: “A response to a drug which is noxious and unintended and which occurs at doses normally used in man for prophylaxis, diagnosis, or therapy of disease or for modification of physiological function.”

Unexpected Adverse Drug Reaction - An unexpected ADR is an ADR, the nature or severity of which is not consistent with the applicable product information (i.e., Sections 7 and 8 of the current IB for ITF2357 Givinostat Hydrochloride Monohydrate).

#### Serious Adverse Event:

An SAE (experience) or reaction is any untoward medical occurrence that at any dose:

- is fatal (results in the outcome death)
- is life-threatening\*
- requires in-patient hospitalisation or prolongation of existing hospitalisation
- results in persistent or significant disability/incapacity
- is a congenital anomaly/birth defect
- is medically significant or requires intervention to prevent one or other of the outcomes listed above

\*The term “life-threatening” refers to an event in which the subject is at risk of death at the time of the event; it does not refer to an event that hypothetically may cause death if it is more severe.

In addition, any suspect of transmission of infective agents through study drug must be reported to the Sponsor as a SAE as medically significant event.

Other important medical events that may not be immediately life-threatening or result in death or hospitalisation, based upon appropriate medical judgment, are considered SAEs if they are thought to jeopardize the subject and/or require medical or surgical intervention to prevent one of the outcomes defining a SAE.

A pre-planned hospitalisation should not be considered an SAE.

A Suspected Unexpected Serious Adverse Reaction (SUSAR) is referred to an ADR that complies with both the definitions of “serious” and “unexpected.”

#### ***12.9.2 Adverse Event Reporting***

The Investigators or their designees are requested to collect and assess any spontaneous AE reported by the subject or their parent/legal guardian and to question the subject or their

parent/legal guardian about AEs and under current illnesses at each visit during the treatment period and any follow-up visit performed to monitor any drug-related AE that is still ongoing beyond the last scheduled visit until recovery. The questioning of subject or their parent/legal guardian regarding AEs is generalized such as: “*How have you been feeling since your last visit?*”

Any AE occurring from the Informed Consent signature up to the first study drug intake will be recorded on the medical history section of the CRF as baseline condition, while any AE occurring after a subject has intake the first study treatment up to the follow-up study visit, whether volunteered by the subject/parent/legal guardian, discovered during general questioning by the Investigators or detected through physical examination, laboratory test or other means will be recorded on the specific section of the CRF.

Each AE will be described by:

- seriousness;
- duration (start and end dates);
- severity;
- relationship with the study drug;
- action taken.

The severity of AE should be assessed and graded according to the most recently published National Cancer Institute Common Terminology Criteria for AE (CTCAE v. 4.03, 14th June 2010).

The relationship with the study drug should be assessed as:

- related to study drug;
- not related to study drug;
- unknown.

The assessment of the relationship of an adverse event with the administration of study drug is a clinical decision based on all available information at the time of the completion of the CRF.

An assessment of “*Related*” indicates that there is a reasonable suspicion that the AE is associated with the use of the study drug.

An assessment of “*Not related*” would include the existence of a clear alternative explanation, or non-plausibility.

An assessment “*Unknown*” indicates there is not a reasonable suspicion that the AE is associated with the use of the study drug and at the same time there is not the existence of a clear alternative explanation or non-plausibility. In this case, Investigator has to collect all possible information in order to assess the relationship with the study drug, particularly in case of SAEs.

Factors to be considered in assessing the relationship of the AE to study drug include:

- The temporal sequence from study drug administration;
- The recovery on discontinuation and recurrence on reintroduction;
- The concomitant diseases;
- The evolution of the treated disease;
- The concomitant medication;
- The pharmacology and PK of the study drug;
- The presence of an alternative explanation.

Abnormal Laboratory Findings and Other Objective Measurements:

Abnormal laboratory findings and other objective measurements should not be routinely captured and reported as AEs as they will be collected and analysed separately in the eCRF. However, abnormal laboratory findings and other objective measurements that meet the criteria for an SAE, result in discontinuation of the study drug or require medical intervention, or are judged by the Investigator to be clinically significant changes from baseline values should be captured and reported on the AE pages of the eCRF.

When reporting an abnormal laboratory finding on the AE pages of the eCRF, a clinical diagnosis should be recorded in addition to the abnormal value itself, if this is available (for example “anaemia” in addition to “haemoglobin = 10.5 g/dl”).

Baseline Medical Condition:

Medical conditions present at the screening visit, that do not worsen in severity or frequency during the study are defined as baseline medical conditions and are not AEs. These medical conditions should be adequately documented on the appropriate page of the eCRF, i.e., the medical history page. However, medical conditions present at the initial study visits that worsen in severity or frequency during the study should be recorded and reported as AEs.

### ***12.9.3 Serious Adverse Event Reporting***

Any SAE, including death from any cause that occurs after subject/parent/legal guardian have signed the Informed Consent and up to the follow-up visit (regardless of relationship to study drug/comparator) must be reported by the Investigators to the Sponsor within 24 hours of learning of its occurrence.

Serious adverse event reports must be made whether or not the Investigator considers the event to be related to the investigational drug.

Related SAEs **must** be collected and reported regardless of the time elapsed from the last study drug administration, even if the study has been closed.

As soon as an AE becomes serious, it will be recorded in the AE section of the eCRF and in the SAE form that will be automatically opened if the answer to the question “Was adverse event serious?” in the AE section is “yes.” A paper SAE Form will be also available as backup.

Initial completion and follow-up reporting updates of the SAE eCRF page within the Electronic Data Capture (EDC) system will automatically send the SAE report directly to the Syneos Health Global Safety and Pharmacovigilance (GSPV) via secure email.

This automated e-mail alert process supports the Investigator in the notification of SAEs to the Syneos Health GSPV. Sufficient details must be provided to allow for a complete medical assessment of the AE and independent determination of possible causality. The Investigators are obliged to pursue and provide additional information as requested by Italfarmaco S.p.A. Corporate Drug Safety, or its designee or the Medical Monitor of the study or Clinical Research and Development Director, or his designee.

The Investigator must notify the Sponsor and his designee of the SAE by completing the SAE reporting form available within the eCRF or, as a backup ONLY in case of technical issues, by faxing the SAE reporting form at the number specified below, within 24 hours of a SAE; then, only in case of SAE notification by fax (backup system) the Investigator must confirm any SAE notifications by mailing to the mail address or phoning to the phone number specified below:

Syneos Health Pharmacovigilance Email: [[contact]](mailto:[contact])

Syneos Health Pharmacovigilance Fax Numbers:

North America: [contact]  
All other countries: [name]

If notification cannot be made via these means due to technical delivery problems, initial notification may be made by telephone, using the SAE [contact]**

The same procedure must be applied to the SAE follow-up information. Preliminary reports of SAEs must be followed by detailed descriptions later on, including clear and anonymized photocopies of hospital case reports, consultant reports, autopsy reports, and other documents when requested and applicable.

Appropriate remedial measures should be taken to treat the SAE and the response should be recorded. Clinical, laboratory and diagnostic measures should be employed as needed in order to determine the etiology of the problem. All SAEs will be followed until the Investigator and Sponsor agree the event is satisfactorily resolved.

Any SAE that is not resolved by the end of the study or upon discontinuation of the subject's participation in the study is to be followed until it either resolves, stabilizes, returns to baseline values (if a baseline value is available), or is shown to not be attributable to the study drug or procedures.

All serious and unexpected AEs that are associated with the use of the study drug (SUSARs) will be notified by the Drug Safety Manager to the Ethic Committees or Institutional Review Board and competent authority within the required time and following procedures required by applicable laws. It is imperative that the Sponsor be informed as soon as possible, so that reporting can be done within the required time frame.

#### ***12.9.4 Overdose***

In general, a drug overdose in a clinical study is defined as the accidental or intentional use of a drug or medicine in an amount exceeding the protocol defined dose. The Investigator must immediately notify the Sponsor of any occurrence of overdose with study drug. In this study, if an AE is associated with ("results from") the overdose of givinostat/placebo, the AE is reported as a SAE, even if no other criteria for seriousness are met.

If a dose of givinostat/placebo meeting the protocol definition of overdose is taken without any associated clinical symptoms or abnormal laboratory results, the overdose is reported as a non-serious Event of Clinical Interest, using the terminology “accidental or intentional overdose without adverse effect.”

Any instance of overdose (suspected or confirmed, with and without an AE) must be reported to the Sponsor within 24 hours and, only in case of AEs, it must be fully documented as a SAE. Details of any signs or symptoms and their management should be recorded in the SAE Form including details of any antidote or systematic treatment administered. Any signs or symptoms of over-dosage will be treated symptomatically.

Any other situations putting the subject at risk of an adverse reaction, such as misuse and abuse, medication errors, suspect of transmission of infective agents must be reported to the Sponsor within 24 hours and be fully documented as a SAE.

#### ***12.9.5 Pregnancy reporting***

Since it is possible to randomize adolescent fertile trial male subjects in this trial, the subject must be informed by the investigator that if it is suspected that his partner becomes pregnant during the study treatment or within 3 months days after the study treatment, he should inform the site personnel immediately of this pregnancy.

If the Investigator is made aware that the partner of a subject who is participating to the study become pregnant, he/she is required to report within 24 hours the pregnancy, using the Pregnancy Notification Form available in the Investigator Study File, to Syneos Health Pharmacovigilance by mailing to the mail address or faxing numbers specified below:

- Syneos Health Pharmacovigilance Email:

### **13 STATISTICAL ANALYSIS**

A Statistical Analysis Plan (SAP) will be prepared prior to the first planned interim analysis to provide full details on the methods described here and provide a complete description of the data presentations required for this study. Changes to the statistical analysis planned in this protocol will be described in the SAP along with the rationale for the changes.

The statistical evaluation will be performed using the latest available version of the Statistical Analysis Software (SAS®) (SAS Institute, Cary, NC).

All data will be listed, and summary tables will be provided. Summary statistics will be presented by dose group. For continuous variables, data will be summarized with the number of subjects (N), mean, SD, median, minimum, and maximum by treatment group. For categorical variables, data will be tabulated with the number and proportion of subjects for each category by treatment group.

#### **13.1 Overall Statistical Strategy**

This trial design a single planned interim analysis. The interim will be governed by an IDMC. The interim analysis will be performed when the first N=50 subjects randomised in the target population have reached the 12 month time point. The purpose of this interim is to solely assess fertility on VL MFF and execute a blinded sample size re-estimation procedure, **there will be no formal analyses for efficacy and no early stopping for efficacy and hence no alpha spend.**

#### **13.2 Determination of Sample Size**

The sample size was originally calculated to provide 90% power and a 1-sided alpha of 2.5% to detect a true difference between givinostat and placebo in the target population in 4SC 18 month change from baseline of 3 seconds, assuming a common SD of 6 seconds. The

estimated SD is based on publicly available Phase 3 study data on ataluren and drisapersen in subjects with DMD in addition to internal Italfarmaco data.

The pre-planned interim analysis was performed in January 2020; it was concluded by the IDMC that futility on VLFF was not met and the trial should continue; hence the pre-planned blinded sample size re-assessment was performed. The blinded within treatment SD for the change in 4CS from baseline to 18 months was estimated to be 3.094 seconds, approximately half of that assumed in the original power calculation. Based on this SD estimate, the revised sample size (utilizing a 2:1 randomisation scheme) N= 102 was calculated to provide 90% power and a 1-sided alpha of 2.5% to detect a true difference between givinostat and placebo in the target population, in 4SC 18 month change from baseline, of 2 seconds. With an estimated drop-out rate of 8%, a total of 110 subjects in the target population (Group A) will be randomized.

For the MR cohort, the blinded SD estimate was 5.941%, being in line with the 6% SD assumed in the original power calculation, hence all the subjects in the target population will be included in the MR cohort.

A total of 110 male ambulant subjects will be randomised in the target population (Group A). Up to 50 subjects (about 35% of the overall population) outside of the target may also be recruited into the study (Group B). The overall subjects population (Group A + Group B) will provide supportive data.

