Sample size calculation:	
The sample size (utilizing a 2:1 randomisation scheme) is calculated to provide 90% power and a 1-sided alpha of 2.5% to detect a true difference between givinostat and placebo in the target population, in 4SC 18 month change from baseline, of 3 seconds, assuming a common standard deviation (SD) of 6 seconds. The estimated SD is based on publicly available Phase 3 study data on ataluren and drisapersen in subjects with DMD in addition to internal Italfarmaco S.p.A data.
 
Vastus lateralis muscles fat fraction (VL MFF) assessed via MRS is the first key endpoint in the MR cohort and will be formally assessed in the target population at 12 months. Based on internal Italfarmaco S.p.A. data, a total of N=99 subjects will be sufficient to provide 80% power to detect a 55% reduction in the annual mean increase in MFF (of 6.6%) with givinostat as compared to placebo with a 1-sided alpha of 2.5% and assuming an SD for the change from baseline in MFF of 6%.
 
The pre-planned interim analysis was performed in January 2020, concluding that futility was not met and the trial should continue, and thus a pre-planned blinded sample size re-calculation was performed. The within treatment SD for the change in 4SC from baseline to 18 month was estimated to be 3.094 seconds, approximately half of the SD that as assumed in the original power calculation. With this revised SD estimate, N= 102 (on 2:1 basis) subjects is sufficient to provide 90% power to detect a true difference in 4SC of 2 seconds between givinostat and placebo in the target population at a 1-sided

	
alpha of 2.5%. With an estimated drop-out rate of 8%, a total of 110 subjects in the target population (Group A) will be randomized.
 
For the MR cohort, the blinded SD estimate was 5.941%, being in line with SD assumed in the original power calculation for VLFF, hence all the subjects in the target population will be included in the analysis of the MR cohort.

Interim analysis:
	
One formal interim analysis is planned and will be overseen by the IDMC in order to ensure study integrity ; this is to assess futility on VLFF and, if not futile, execute a blinded sample size reestimation.

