	
degree of increase in sample size will maintain 90% power, and for a 40% increase in SD power will be maintained at 80%.
 
 
• With respect to VL MFF, a similar approach will be applied; the within treatment SD for the change from baseline will be estimated as <math>\hat{\sigma}_{within} = \sqrt{\hat{\sigma}_{overall}^2 - \left(\frac{\Delta}{2}\right)^2}</math> where <math>\hat{\sigma}_{overall}</math> is the overall SD for the change from baseline in MFF and <math>\Delta</math> is the hypothesized treatment effect, i.e. <math>\Delta = 3.63\%</math> (i.e. 55% of 6.6%). Dependent upon the blinded SD estimate, the sample size may be decreased or increased to maintain 90% power. Any increase in sample size require to assess VL MFF will also be limited to 1.5 times the required target population sample size stated in the preceding power calculation, to a maximum of <math>1.5 \times 99 = 150</math> subjects.
 
 
At the interim futility analysis, there will be no efficacy assessment, no unblinded analysis of the primary endpoint and, hence, no alpha spend nor early stopping of the study for efficacy.
 
The interim took place as planned on 14th January 2020 and included 50 patients with 12 month data and 37 with 18 month data. The independent data monitoring committee (IDMC) meeting to review the VL MFF data for futility took place on 23rd January 2020 and concluded that futility was not met and the trial should continue. The sample size reassessment therefore took place, with estimated overall SDs of 3.094 seconds and 5.941% for the change from baseline in 4SC at 18 months and the change from baseline in VL MFF at 12 months respectively.
 
The revised sample size (utilizing a 2:1 randomisation scheme) N=102 was calculated to provide 90% power and a 1-sided alpha of 2.5% to detect a true difference between givinostat and placebo in the target population, in 4SC 18 month change from baseline, of 2 seconds, with the blinded SD estimates during the interim analysis of 3.094 seconds. With an estimated drop-out rate of 8%, a total of 110 subjects in the target population (Group A) will be randomized.
 
For the MR cohort, since the blinded SD estimate was 5.941%, all the subjects in the target population will be part of the MR cohort.
 
Since the interim only assessed futility on VLFF and executed a blinded sample size reestimation, no alpha was spent and, hence the analysis of the primary endpoint conducted at the end of the trial will continue to be assessed at the 0.025 1-sided level.

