2.5 Sample Size

The sample size was originally calculated to provide 90% power and a 1-sided alpha of 2.5% to detect a true difference of 3 seconds between givinostat and placebo in the target population 4SC change from baseline to 18 months, assuming a common standard deviation (SD) of 6 seconds. The estimated SD was based on publicly available Phase 3 study data on ataluren and drisapersen in subjects with DMD in addition to internal Italfarmaco data. This gave rise to an estimated sample size of N=192 subjects in the target population.

Based on internal Italfarmaco data, a total of N=99 subjects was originally calculated as sufficient to provide 80% power to detect a 55% reduction in the annual mean increase in VL MFF (of 6.6%) with givinostat as compared to placebo with a 1-sided alpha of 2.5% and assuming an SD for the change from baseline in VL MFF of 6%.

The pre-planned interim analysis took place in January 2020 based upon the first 50 randomised subjects reaching 12 months of treatment. It was concluded by the IDMC that futility on VL MFF was not met and the trial should continue. Therefore, the pre-planned blinded sample size re-assessment was performed. This provided a revised, blinded within treatment SD estimate for the change in 4CS from baseline to 18 months of 3.094 seconds, approximately half of that assumed in the original power calculation. Based on this revised SD estimate, the revised sample size (utilising a 2:1 randomisation scheme) is N=102. This provides 90% power and a 1-sided alpha of 2.5% to detect a true difference of 2 seconds between givinostat and placebo in the target population, for the change from baseline in 4SC at 18 months.

With an estimated drop-out rate of 8%, a total of 110 male ambulant subjects will be randomized in the target population (Group A). Up to 50 subjects (about 35% of the overall population) outside of the target population may also be recruited into the study (Group B). The overall subjects population (Group A + Group B) will provide supportive data.

For the MR cohort, the blinded SD estimate was 5.941%, being in line with the 6% SD assumed in the original power calculation, hence all the subjects in the target population will be included in the MR cohort.

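### The revised sample size of 102 does not give 90% power from its stated inputs, and its SD of 3.094 s is labelled both within-treatment and overall

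*Protocol*

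**What the plan says.** Protocol 13.2 gives the SD and the sample size together: "The blinded within treatment SD for the change in 4CS from baseline to 18 months was estimated to be 3.094 seconds", and then "Based on this SD estimate, the revised sample size (utilizing a 2:1 randomisation scheme) N= 102 was calculated to provide 90% power" at one-sided 2.5%, the difference being "in 4SC 18 month change from baseline, of 2 seconds". Allocation is 2:1. An 8% drop-out allowance takes the target population to 110 randomised.

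The sample-size part of the synopsis agrees: "The within treatment SD for the change in 4SC from baseline to 18 month was estimated to be 3.094 seconds" and "With this revised SD estimate, N= 102 (on 2:1 basis) subjects is sufficient to provide 90% power to detect a true difference". Protocol 6.2 says the same, and so does SAP 2.5: "Based on this revised SD estimate, the revised sample size (utilising a 2:1 randomisation scheme) is N=102".

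The synopsis account of what the interim found labels the figure differently: "with estimated overall SDs of 3.094 seconds and 5.941% for the change from baseline in 4SC at 18 months".

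The synopsis, Protocol 13.10.1 and SAP 2.6 all give the same blinded conversion. The within-treatment SD is the square root of the overall variance minus (Δ/2)², with Δ set at 3 s for 4SC.

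**The concern.** There are two linked problems. First, the stated SD, difference, allocation and alpha should return N=102 at 90% power, and they do not. Second, the conversion formula makes the overall SD larger than the within-treatment SD for any non-zero Δ, so 3.094 s cannot be both.

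This calculation reduced the primary target population from 192 to 102. If 3.094 s is the within-treatment SD, the chance of missing a true 2 s effect is 13–14% rather than 10%. A borderline or null 4SC result would then be judged against a power that the stated inputs do not support. If 3.094 s is the overall SD, the power may be adequate, but the SD named as its basis in four places is wrong.

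**Working it through.** **Inputs.** One-sided alpha 2.5%, power 90%, difference 2 s, SD 3.094 s, 2:1 allocation, N=102 (Protocol 13.2, SAP 2.5). Original design: 3 s, SD 6 s, N=192 (Protocol 6.2, SAP 2.5). Conversion formula with Δ = 3 s: Protocol 13.10.1, SAP 2.6.

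**Formula.** For 2:1 allocation under the normal approximation, the placebo group needs n = 1.5 × [SD × (1.960 + 1.282) / difference]², rounded up, and N = 3n. The sum of the normal quantiles is 3.2415.

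**Step 1: reproduce the plan's other figures.**
- Original 4SC design: 1.5 × (6 × 3.2415 / 3)² = 63.04, so n = 64 and N = 192, as stated.
- VL MFF (3.63%, SD 6%, 80% power): n = 33 and N = 99, as stated.

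The formula therefore matches the sponsor's own.

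**Step 2: the revised design as written.** 1.5 × (3.094 × 3.2415 / 2)² = 37.72, so n = 38 and N = 114. With the noncentral t, N = 117.

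**Step 3: power at N=102 (68:34).** The standard error is 3.094 × √(1/68 + 1/34) = 0.650, and 2 / 0.650 = 3.078. Power is Φ(3.078 − 1.960) = 86.8%, or 86.2% with the noncentral t. For 90% power at this N, one of the following must hold:
- the difference is 2.11 s (normal) or 2.13 s (t);
- the SD is 2.94 s (normal) or 2.91 s (t).

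If all 110 randomised subjects were evaluable (73:37), power would be 89.3% (normal) or 88.8% (t).

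**Step 4: which readings return 102?** N is by the normal approximation, and power is for a 2 s difference.

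| Reading of 3.094 s | Within-treatment SD | N for 90% | Power at N=102, 2:1 (normal / t) |
|---|---|---|---|
| Within-treatment, 2:1 | 3.094 | 114 | 86.8% / 86.2% |
| Within-treatment, 1:1 | 3.094 | 102 | not applicable (51:51 gives 90.4% / 89.8%) |
| Overall, prespecified Δ = 3 s | √(9.573 − 2.25) = 2.706 | 87 | 94.0% / 93.6% |
| Overall, Δ = 2 s | √(9.573 − 1) = 2.928 | 102 | 90.2% / 89.6% |

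Of the 2:1 readings tried, only the last returns 102, and the documents do not describe it.

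**Step 5: the constant in the conversion.** The between-group share of the overall variance is p(1 − p)Δ². At 1:1 this is Δ²/4, which is the (Δ/2)² in the plan. At 2:1 it is (2/3)(1/3)Δ² = (2/9)Δ². Correcting it has a small effect:
- Overall SD 3.094 s, Δ = 2 s: within-treatment SD 2.947, N = 105, power at 102 of 89.8% (normal) or 89.3% (t).
- Overall SD 3.094 s, Δ = 3 s: within-treatment SD 2.752, N = 90, power at 102 of 93.3% or 92.9%.
- 3.094 s as the output of the prespecified formula: overall SD √(9.573 + 2.25) = 3.438, corrected within-treatment SD √(11.823 − 2) = 3.134, power at 102 of 86.0% or 85.3%.

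**The case against.** The strongest reply is that under-powering is not established. The synopsis label (overall SD), with the new 2 s effect in the formula, gives exactly 102 at 2:1 and 90.2% power. On that reading the sample size is sound and the faults are a repeated wrong label and an unrecorded change of Δ. This stands: the shortfall depends on 3.094 s being the within-treatment SD. It does not save the text, because the label in the synopsis sample-size paragraph, Protocol 6.2, Protocol 13.2 and SAP 2.5 would then be wrong.

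The match with a 1:1 calculation might suggest that the allocation ratio was dropped. The documents cannot show this, and the match holds only under the normal approximation.

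The primary ANCOVA adjusts for baseline 4SC and other covariates, which could recover power. As an assumption, a multiple correlation of about 0.31 (normal) or 0.34 (t) would restore 90% at N=102. The sample-size text claims no such gain and gives no correlation.

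The SD is itself imprecise. The synopsis reports 37 subjects with 18-month data; assuming roughly normal values, the 95% interval around 3.094 s runs from about 2.5 to 4.0 s. That is wider than the discrepancy at issue. It limits how much weight any planned power can bear, but it does not explain why the stated inputs and output disagree.

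The type I error, the significance threshold and the planned confidence interval are unaffected.

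**Conclusion.** The point holds: the sample-size statement is wrong as written. With 3.094 s as the within-treatment SD, N=102 at 2:1 gives 86–87% power for 2 s, and 90% needs 114 (normal) or 117 (t) evaluable subjects. With 3.094 s as the overall SD and the prespecified Δ of 3 s, N would have been 87, with about 94% power at 102. With 3.094 s as the overall SD and Δ of 2 s, N=102 and 90% agree, but the within-treatment label and the stated Δ do not. The documents do not show which applies.

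These figures assume an unadjusted two-group comparison with a common SD, as the sample-size text does, and all 102 subjects evaluable. The 1:1 constant in the conversion is a secondary error, worth about one percentage point of power or less.

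**What to change.** State four numbers together: the blinded overall SD of the 18-month change, the Δ entered in the conversion, the resulting within-treatment SD, and the power at N=102 with 2:1 allocation. Use (2/9)Δ² in the conversion. Then:

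- **If 3.094 s is the within-treatment SD:** replace the 90% claim with about 86% power for 2 s, or 90% for about 2.1 s, and report the overall SD from which it came.
- **If 3.094 s is the overall SD:** correct the label wherever it is called within-treatment, give the derived SD, and say whether Δ was 2 s or 3 s. If it was 2 s, record this as a departure from the prespecified 3 s, with the reason.

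The wording changes fall in the Protocol synopsis, 6.2, 13.2 and 13.10.1, and in SAP 2.5 and 2.6. Enrolment, data and the primary analysis are unchanged. The cost is a short clarification and possibly a slightly less favourable stated power.
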